3.2. Bronchoscopy In-vivo Pre-Clinical Study

Title: Acute Evaluation of the Auris Robotic Endoscopic System (ARES) for Bronchoscopy Start/Complete dates: 2/20/2014 to 5/01/2014 Objectives:

• To acutely evaluate the following in bronchi in vivo in porcine models:

- The safety profile of the procedure
 - Document any adverse events or findings
- The performance of the Auris system
 - Navigation
 - Visual
 - Movement
 - Biopsy

 To evaluate the ability for an operator/physician to consistently/accurately control and navigate in an animal bronchial tree

Results:

- Number of animals
 - **1**0
- Biopsy evaluation
 - Successful use of both biopsy forceps and needle aspiration devices
- Navigation
 - Successful robotic navigation throughout the bronchial tree
- o Safety
- One pneumothorax
 - The physician user was navigating without vision and testing peripheral reach of the ARES system.
- Emergency removal successful

Conclusion

- Operators/physicians can be trained to successfully navigate throughout the bronchial tree with the ARES system.
- \circ The ARES system appears to be safe with proper usage including navigation with vision
- The ARES system appears to provide a means for successful tissue biopsy using forceps and needle aspiration devices

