9.3. Primary Safety Endpoint

Device related adverse events (AEs)

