Procedure-Related Adverse Event: an adverse event is considered to be procedure-related when, in the judgment of the Investigator; it is reasonable to believe that the event is associated with the assigned study procedure and is not specific to the **AURIS ROBOTIC ENDOSCOPY SYSTEM (ARES)** used. Other products, surgical techniques, or medications required specifically for the procedure are likely to have contributed to the occurrence of the event.

Concomitant Medication-Related Adverse Event: an adverse event is considered to be concomitant medication related when, in the judgment of the Investigator, it is reasonable to believe that the event is associated with concomitant medications used in conjunction with the **AURIS ROBOTIC ENDOSCOPY SYSTEM (ARES)** and is not otherwise specific to the **AURIS ROBOTIC ENDOSCOPY SYSTEM (ARES)** (e.g. bleeding associated with anticoagulation medication).

Pre-Existing Condition-Related Adverse Event: an adverse event is considered to be related to a pre-existing condition when, in the judgment of the Investigator, it is reasonable to believe that the event is associated with the subject's pre-existing condition and is not specific to the AURIS ROBOTIC ENDOSCOPY SYSTEM (ARES) or procedure. Pre-existing conditions that are aggravated or become more severe during or after the procedure should be evaluated on a case-by-case basis to

determine if the event may be more appropriately classified as device-related or procedure-related.

Auris Surgical Robotics, Inc., or its designee, in cooperation with the Investigator, will assess all adverse events considered to be device-related for potential reportability to the FDA and other regulatory authorities as an Unanticipated Adverse Device Effect (UADE).

The Investigator should follow all unresolved serious adverse events until the events are resolved, the subject is lost to follow-up, the subject has withdrawn consent, or the adverse event is otherwise explained.

For purposes of this study, the following events are not likely to be device-specific adverse events, because they are typical procedure/anesthesia related adverse events normally expected to occur in conjunction with these types of bronchoscopic procedures / post-procedure, or are associated with customary, standard care of subjects undergoing these procedures:

- Any pre-planned surgical procedures
- Bleeding
- Pneumothorax
- Post-procedure respiratory insufficiency

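### Section 14.1 tells the site in advance that pneumothorax is unlikely to be device-specific, which discourages device attribution and can lower the Section 9.3 primary safety count

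*Protocol*

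**What the plan says.** **Animal evidence (Protocol, Section 3.2).** Ten animals were studied and the safety results list "One pneumothorax". The only circumstance given is: "The physician user was navigating without vision and testing peripheral reach of the ARES system". No causality rating is recorded. The study's conclusion is conditional: "The ARES system appears to be safe with proper usage including navigation with vision".

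**Attribution guidance (Section 14.1).** The site is told that "the following events are not likely to be device-specific adverse events, because they are typical procedure/anesthesia related adverse events normally expected to occur" with this kind of bronchoscopy. Pneumothorax, bleeding and post-procedure respiratory insufficiency are on the list. The closing paragraph of the section calls the list guidance for adverse event reporting. It asks the investigator to use clinical judgment and says the investigator may decide that the listed events should be reported.

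**Endpoint.** Section 9.3 gives the primary safety endpoint as "Device related adverse events (AEs)". The synopsis gives it as device-related or procedure-related events. Both give complications unrelated to the device as the secondary safety endpoint (Section 9.4 in the body).

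**Relatedness rating.** Section 14.1 asks for the investigator's view of each event's relationship to treatment and procedure. Section 14.2.1 requires serious events, and events potentially related to device or procedure, to be recorded with their relationship to device, procedure, medication and pre-existing condition.

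**The concern.** The study has one arm and no control, so nothing in the design separates harm from the robotic scope from harm from bronchoscopy and biopsy in general. Only the investigator's attribution does that. Section 14.1 gives that judgment a starting point for pneumothorax before any patient is treated, and the starting point leans away from the device.

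The wording also matches a category. Section 14.1 defines a procedure-related event as one that is not specific to the ARES, so describing pneumothorax as unlikely to be device-specific points it to that category. The device-related definition requires, among other things, that the event is unlikely to be due to other procedures, so the guidance bears on that test as well.

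The protocol's own animal study recorded a pneumothorax while the scope was being driven towards the periphery, and this study targets peripheral lesions. If such events are classed as procedure-related, the Section 9.3 count is too low. A reader who sees only that count would underestimate how often the device may have contributed.

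**Working it through.** The protocol states no pneumothorax rate for this procedure, no hypothesis and no sample size calculation, so there is no figure of its own to reproduce. The checks below set out what the evidence shows and where an event lands.

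**1. Strength of the earlier evidence (exact Clopper-Pearson 95% intervals)**
- Animals (Section 3.2): 1/10 = 10%, interval 0.3% to 44.5%.
- Human bronchoscopy pilot (Section 1.1): 0/15, upper limit 21.8%.
- Fisher's exact test of 1/10 against 0/15: p = 0.40.

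One animal event does not establish a rate or a cause. The clean pilot does not rule out a device contribution.

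**2. Where a pneumothorax is counted**

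| Investigator's classification | Section 9.3 | Synopsis | Section 9.4 |
|---|---|---|---|
| Device-related | primary | primary | no |
| Procedure-related, not device-related | not counted | primary | yes |

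The Section 14.1 guidance pushes events from the first row to the second. That changes the primary count under Section 9.3 and leaves it unchanged under the synopsis.

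**3. How many events are exposed to this.** With N = 60 (the maximum in Section 5.2) and an assumed rate p, expected events = 60p and P(at least one) = 1 − (1 − p)^60.

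| p | Source | Expected events | P(at least one) |
|---|---|---|---|
| 0.1% | Section 1.2.1, lower end | 0.06 | 6% |
| 1% | Section 1.2.1, upper end | 0.6 | 45% |
| 2% | assumption | 1.2 | 70% |
| 5% | assumption | 3 | 95% |

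Section 1.2.1 says its figures exclude biopsy. Section 8.4 plans four needle aspirations and four forceps biopsies per target, so 0.1% to 1% is a low reference for this study. The 2% to 5% range is not in the protocol.

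**4. Effect on the Section 9.3 count.** Suppose three pneumothoraces occur and the device contributed to all three. This is the upper end of the assumed range and an unfavourable case.

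| Classed as procedure-related | Section 9.3 reads | Exact 95% interval |
|---|---|---|
| 0 of 3 | 3/60 = 5.0% | 1.0% to 13.9% |
| 1 of 3 | 2/60 = 3.3% | 0.4% to 11.5% |
| 2 of 3 | 1/60 = 1.7% | 0.04% to 8.9% |
| 3 of 3 | 0/60 | 0 to 6.0% |

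The protocol gives no basis for choosing a row. The direction is fixed: misclassification prompted by the list can only lower the count.

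**The case against.** The case against has several parts, and much of it stands.

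- **The list does not bind.** It says unlikely, calls itself guidance and leaves the decision to the investigator. The device-related definition still covers events to which the system contributed, and individual ratings are already required. This stands: attribution is discouraged, not barred. The advance steer remains, and the remark that the investigator may decide to report these events makes reporting look optional, which sits badly with Section 14.2.1.
- **The events do not vanish.** Every patient has a chest X-ray within two hours. Serious events go to the sponsor within 24 hours whatever their cause, and a non-device event falls under Section 9.4. This stands: the risk is mislabelling, not loss.
- **The synopsis keeps procedure-related events in the primary endpoint.** This stands and decides the consequence. The bias arises only under Section 9.3.
- **Biopsy is an obvious competing cause.** True. It supports judging each event on its facts and does not justify a presumption set beforehand.

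A reader might infer that Section 3.2 shows the device causes pneumothorax, or that it contradicts Section 14.1. The documents do not support this. Section 3.2 reports one animal event under navigation without vision, gives no causality rating, and sets those conditions apart from proper use. Section 8.4 plans direct visualization with electromagnetic navigation.

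A reader might also infer that device pneumothoraces would escape review as unanticipated adverse device effects, because the sponsor "will assess all adverse events considered to be device-related for potential reportability". By the definition in Section 19.2, such an effect must be serious and not already identified in nature, severity or incidence. Lung collapse is already listed in Section 1.2.1, so an ordinary pneumothorax would usually not qualify however it was attributed.

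**Conclusion.** The concern holds in a limited form. The guidance in Section 14.1 introduces a written presumption against the device for pneumothorax, bleeding and respiratory insufficiency, in a design where investigator attribution is the only means of separating device harm from procedure harm. Under Section 9.3 the primary safety count is biased downward and the affected events move to Section 9.4. Under the synopsis they remain in the primary endpoint.

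The size cannot be fixed from the protocol. Between 0.06 and 0.6 pneumothoraces are expected in 60 patients at the Section 1.2.1 range, and 1.2 to 3 at an assumed 2% to 5%. The contrast between 0/60 and 3/60 is a worst case: it needs three events, a device contribution to all three, and misclassification of all three. It should not be read as a forecast. In a feasibility study with no hypothesis, this is a wording defect that affects how the safety result reads, and it is worth correcting because the correction is nearly free.

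**What to change.** 1. In Section 14.1, retitle the list as anticipated events. State that inclusion has no bearing on relatedness or on whether an event is reported. Remove the suggestion that reporting these events is optional.
2. State one primary safety endpoint in both the synopsis and Section 9.3. The choice decides whether procedure-related pneumothoraces are primary.
3. Report the total number of pneumothoraces, whatever their attribution, next to the device-related count.

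The cost is a few sentences of protocol text and one extra line in the safety table. The X-ray and the relatedness rating are already planned. The device-related count may become slightly less favourable.

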3.3. Ureteroscopy Clinical Pilot Study

Title: Robotic Endoscopy Pilot Study for the treatment of Renal Calculi

Start/Complete dates: 6 to 10 June 2014

Objectives/Study Design:

- The primary objective of this study is to evaluate the safety and performance of the ARES for the treatment of renal and/or ureteral calculi.
 - This is an unblinded, single-arm, single site study.
 - The study was approved by the ethics committee at the Muljibhai Patel Urological Hospital.

Results

- o 16 patients
 - 24 stones removed
 - Safety

 \cap

No surgical or post-operative complications

Conclusions

• Operators/physicians can be trained to successfully navigate throughout the bronchial tree with the ARES system.

ARES Bronchoscopy Study	CONFIDENTIAL	October 5, 2017
Page 22 of 55		

- \circ The ARES system appears to be safe with proper usage including navigation with vision
- There were no unanticipated adverse events from the procedure

3.4. Bronchoscopy Clinical Pilot Study

Title: Performance and safety evaluation of a robotic bronchoscopy system for diagnosis of suspected lung cancer: A Clinical Pilot Study

Start/Complete dates: 13 September 2014 to 5 October 2014

Objectives:

- The primary objective of this study is to evaluate the safety and performance of the ARES for the access of suspicious lung cancer lesions
- This is an unblinded, single-arm, single site study
- The study was approved by the ethics committee at the Hospital Clínica Bíblica and WIRB (Western Institutional Review Board)

Results

- o 15 patients
 - Enrolled/completed the study
 - Able to navigate and biopsy from 15 of the 15 (100%) study procedures
- Safety
 - No surgical or post-operative complications

Conclusions

- Operators/physicians can be trained to successfully navigate throughout the bronchial tree with the ARES system.
- There were no unanticipated adverse events from the procedure

4. Study Objective

The objective of this study is to evaluate the performance of the Monarch Robotic Endoscopy Platform, the next generation of Auris Robotic Endoscopy System (ARES) during bronchoscopy procedures. Information obtained during this feasibility study may be used to guide future product development.

Product features may be added and/or revised during the conduct of the study and will be evaluated by the physician. The IRB will be kept informed of any product revisions as appropriate.

The study is a NSR feasibility study with no specific statistical study size or power.

5. Study Design

5.1. Overview

A single-center, prospective, single arm study to evaluate the performance of the ARES System during bronchoscopy procedures. The Auris system will be used in conjunction with a navigational bronchoscopy procedure.

5.2. Sample Size

The study will enroll up to 60 patients.

It is expected that enrollment will take up to 6 months.

5.3. Investigational Site

Figure 5. Schematic of Study Design

6. Study Population

6.1. Selection Criteria

The following pages outline the specific inclusion and exclusion criteria for the study. Before study enrollment, a patient must meet all of the inclusion and none of the exclusion criteria.

6.1.1. Pre-Procedure Inclusion Criteria

All subjects are required to meet the following inclusion criteria in order to be considered eligible for participation in this Study:

Pre-Operative Inclusion Criteria	 1. 18 to 80 years of age; 2. Capable and willing to give informed consent;
	Acceptable candidate for an elective, non-emergent Bronchoscopic procedure;
	 Solid peripheral lung lesions suspected of malignancy, between 1.5- 7cm in size identified on thin slice CT scan with 30 days of the intended bronchoscopy

6.1.2. Pre-Procedure Exclusion Criteria

Subjects will be excluded from participating in this Study if they meet any of the following exclusion criteria prior to initiation of the endoscopic procedure.

Pre-Operative Exclusion Criteria	1. 2. 3. 4.	Medical contraindication to bronchoscopy; Ground glass opacity lesions on pre-procedure CT Participation in any other clinical trial 30 days before and throughout the duration of the study; Uncontrolled or irreversible coagulopathy;
	5. 6.	Female subjects who are pregnant or nursing or those of child-bearing potential refusing a pregnancy test; CT scan done over a month before the bronchoscopy procedure.

6.1.3. Intra-Operative Exclusion Criteria

Subjects will be excluded from participating in this Study if any of the following exclusion criteria occur during the endoscopic procedure:

Intra-Procedure A Exclusion Criteria c	Any presenting condition discovered intra-procedurally that in the opinion of the investigator would make participating in this study not in the patient's best interest.
---	---

6.2. Withdrawal of Subjects

While study withdrawal is discouraged, patients may withdraw from the study at any time, with or without reason and without prejudice to further treatment. In all cases of withdrawal, the reason(s) for withdrawal (if given) will be recorded upon study termination.

In addition, the investigator may withdraw the subject due to any of the following situations:

- adverse event
- any other reason determined by the investigator to be in the best interest of the subject.

Subjects withdrawn from the Study prior to insertion of the ARES should be converted to conventional bronchoscopy. Subjects withdrawn due to an adverse event should be followed until the event has been resolved or is stable, if at all possible.

7. Written Informed Consent

Written Informed Consent must be obtained for all patients who are potential study candidates before any study-specific tests or procedures are performed.

Patients who meet general entry criteria will be asked to sign the study-specific, Institutional Review Board (IRB) -approved Informed Consent form before any study-specific tests or procedures are performed. Study personnel should explain that even if a patient agrees to participate in the study and signs an informed consent form, the ARES may demonstrate that the patient is not a suitable candidate for the study.

A Screening/Enrollment Log will be maintained to document select information about candidates who fail to meet the entry criteria.

8. Study Procedures and Enrollment

8.1. Duration of Subject Participation

Once the subject has completed 6 weeks (±1 week) follow-up without study related adverse events requiring further follow-up, subject will be exited from the study.

8.2. Enrollment

Subjects that meet the pre-operative inclusion/exclusion criteria will be invited to participate in the Study and sign the IRB approved informed consent form. All subjects must provide written informed consent before undergoing any study related activity.

8.3. Assessment Schedule

The following page outlines the required study assessments.

Test/Parameter	Screening/	Pre-	Procedure	Discharge	Follow-up	Follow-	Follow-
	Baseline	Procedure			24±12	up 7±3	up 6±1
					hours	days	weeks
Informed Consent							
	X						
Pregnancy Test (if applicable)	x						
Preliminary Qualification	х						
(inclusion/exclusion criteria)							
Medical History (pulmonary	х						
status)							
Physical examination		х				х	
ECG	x						
Blood test and coagulation	х						
test (PT/INR) ¹							
HRCTScan ²	x						
Fluoroscopy ³			x				
Radial probe Endobronchial			X4				
ultrasound (REBUS) ⁴							
Chest X-ray⁵				X ⁵			
Concomitant medications ⁶	x	x					
Follow-up Form				х	х	х	x
Navigation/control evaluation			x				
Biopsy sample evaluation			х				

Table 1.	Schedule of	Assessments
----------	-------------	-------------

¹ A blood test including the PT/INR coagulation test will be assessed before the procedure.

² The procedure will take place within 30 days of CT scan for participation in the study.

³ Fluoroscopy will be used in conjunction to provide an additional viewing method during the procedure.

⁴ REBUS will be used to confirm the presence of a lesion in patients where additional confirmation is needed.

⁵ Chest X-ray within 2 hours from the conclusion of the procedure.

⁶ Aspirin and clopidogrel will be stopped one week before procedure. Oral anticoagulants will be stopped at least 5 days before and coagulations tests will be performed before procedure. Anticoagulants will be restarted 24 hours

after procedure if no bleeding persists. Subcutaneous anticoagulants will be stopped 24 hours before and restarted 24 hours after procedure if no bleeding persists.

Informed Consent. A study specific, IRB approved written informed consent must be obtained for all patients who are potential study candidates before any study-specific tests or procedures are performed.

Pregnancy Test (if applicable). If there is the potential for pregnancy, a serum pregnancy test will be conducted before entry into the study.

Preliminary qualification (Inclusion/Exclusion criteria). Principal Investigator is responsible for certifying that key personnel have received adequate training to ensure they are aware of the regulations governing human subjects research and understand and adhere to the IRB-approved research protocol. Compliance with these standards provides assurance that the rights, safety, and well-being of human subjects are protected and the integrity of the data collected. Potential study candidates must meet the study specific Inclusion/Exclusion criteria based on the screening assessment. For the purpose of this study, a peripheral lung lesion is defined as a lesion located in a sub segmental branch of the bronchial tree that it cannot be accessed by convex probe endobronchial ultrasound.

Medical history. During the screening/baseline assessment, the investigator or coordinator will record details of medical history as they relate to pulmonary status.

Physical examination. The investigator will perform a brief, directed physical and pulmonary examination and document any preoperative abnormalities. The examination will be repeated at the day 7 post-procedure.

Electrocardiogram (ECG). Stickers will be placed on each arm and leg and to your chest area and a heart tracing is performed to measure electrical activity of your heart.

Blood tests including the PT/INR coagulation test. These tests may be needed before the procedure to ensure that study patients have no problems related to blood clotting. (see above). Bleeding can sometimes occur after bronchoscopy, especially if tissue samples are taken. The study patients will be asked to stop anticoagulants several days prior to the procedure (see Table 1. above).

HRCT scan. CT analysis will require a full inspiratory CT scan. CT Scans should be performed no longer than 30 days pre-procedure as part of screening assessment. Specific CT parameters for scanner model and manufacturer will be provided to the site. De-identified CT scans may be provided to the study sponsor.

Fluoroscopy. Fluoroscopy will be used in conjunction with the bronchoscopy to provide an additional viewing method during the procedure.

Radial probe endobronchial ultrasound (REBUS). REBUS will be used to confirm the presence of a lesion in patients where additional confirmation may be needed.

Chest X-ray. Patients will undergo a routine chest X-ray within 2 hours from the conclusion of the procedure to o rule out complications such as pneumothorax.

Concomitant Medications. Principal investigator will determine relevant disease/procedure specific concomitant medications that is important for a study conduct. Only the relevant medication will be recorded on a rolling medication log or the relevant case report forms.

Follow-up. The 24 hours (\pm 12 hours) follow-up will be a phone consultation, 7 days (\pm 3 days) follow-up will be an office visit and 6 weeks ((\pm 1 week) follow-up will be a phone consultation. During the follow-up, adverse events will be recorded and associated case report forms will be completed.

Navigation/Control evaluation. The system navigation/control will be evaluated and recorded on the procedure CRFs.

Biopsy sample evaluation. Content and adequacy of biopsy samples will be assessed by pathologist or cytotechnologists using the rapid on-site evaluation (ROSE). A preliminary diagnosis will be recorded. The final histopathologic diagnosis will be recorded on the week 6 follow-up CRF.

